10.9. Withdrawal of an Individual Subject

An individual subject will be withdrawn for any of the following:

- An individual subject's decision (the investigator will attempt to determine the reason for the subject's decision.)
- Non-compliance with study procedures to the extent that it is potentially harmful to the subject or to the integrity of the study data.
- The investigator determines that continued participation in the study would not be in the best interest of the subject.

10.10. Replacement of a Subject Who Discontinues Study Treatment

If a subject withdraws after fewer than 12 weeks of study treatment, then they will be replaced. If a subject is replaced, then all of the data will still be included for the safety assessment.

10.11. Safety Monitoring Plan

The data gathered during this study will be monitored by the PI for safety and compliance with protocol-specified requirements.

11. Statistical Considerations

The proposed study is designed as a proof-of-concept study and will employ paired comparison of each subject pre- and post-treatment. With a total of 20 subjects we will have 90% power to detect a 0.1% unit change in intramyocardial lipid content based on an estimated within subject standard deviation of MRS intramyocardial lipid of 0.07% reported by O'Connor and colleagues³⁶. In our prior work, HIV-infected subjects had a mean intramyocardial lipid content of 1.5% whereas controls were 1.0%. Therefore, with this sample size we will have ample power to detect a minimal clinically relevant reduction of 0.3% units or greater following eplerenone therapy.

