Study Agent/ Intervention Description:	Inspra®/Epplerenone (Pfizer Inc [New York City, NY, USA]), 25 mg/day for 1 week, then 50 mg/day for 23 weeks
Primary Objective:	To evaluate the effects of epplerenone on cardiac and hepatic steatosis in people with HIV infection who have high central adiposity.
Secondary Objectives:	To evaluate the effects of epplerenone treatment on biomarkers of inflammation and immune activation.
Primary Endpoints:	1. Improvement of cardiac steatosis as measured by magnetic resonance imaging (MRI) of the intraventricular septum 2. Improvement of hepatic steatosis as measured by MRI of the liver and histopathologic examination of liver biopsy.
Secondary Endpoint:	Reduction of biomarkers of inflammation and immune activation.

Précis

HIV-infected individuals are at higher risk than uninfected people for developing cardiovascular disease. Visceral adipose tissue is also increased in HIV-infected people compared to uninfected individuals. Animal studies suggest that blockade of the mineralocorticoid receptor (MR) may have beneficial effects on cardiovascular and metabolic parameters via inhibition of adipocyte differentiation and triglyceride accumulation. We will examine the effects of the MR antagonist eplerenone (50 mg daily) on HIV-infected adults with abdominal fat accumulation in a 24-week, open-label, proof-of-concept study. Magnetic resonance imaging will be conducted at screening and the final study visit to evaluate cardiac and hepatic steatosis. We anticipate that blocking the effects of increased aldosterone secretion with eplerenone will significantly reduce intramyocardial lipid content and hepatic steatosis in this population. These effects may be accompanied by decreases in visceral adipose tissue, and improvements in dyslipidemia and inflammation, thereby improving cardiovascular health.

1. Background Information and Scientific Rationale

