3.1. Description of the Study Design

This is an open-label pilot study of the effects of eplerenone on 20 HIV-infected subjects who have increased central adiposity and evidence of hepatic steatosis. Eplerenone will be administered for 6 months as follows: 25 mg once daily for 1 week and then 50 mg once daily for the remainder of the study. This is a proof of concept study and therefore the sample size will be relatively small and there will be no control arm. If there is a signal for a beneficial effect of eplerenone, then we will consider design of a larger controlled trial in the future.

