11.1. Statistical Analysis Plan

As previously stated, the primary endpoints for this study will be change in cardiac and hepatic steatosis from initial measurement (pre-treatment) to end of study measurement. This will be tested using a paired t-test, and a two sided p value of < 0.05 will be used for detection of

significance. In addition, we will conduct exploratory analyses to determine if eplerenone therapy is associated with changes in biomarkers of inflammation (eg, MCP-1 and IL-6). We also plan to evaluate potential changes in visceral fat volume with treatment, but these will be exploratory analyses, primarily descript, and which may not be sufficiently powered in this small preliminary trial. Finally we will construct descriptive tables summarizing reported side effects and any observed lab abnormalities observed during the course of study participation in all subjects.

12. Ethics/Protection of Human Subjects

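### The 90% power in Section 11 does not follow from its own inputs (99.0% or more on recalculation), and the assurance for a 0.3% unit reduction rests on an SD of 24-week change that the plan does not give

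*Combined protocol and SAP*

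**What the plan says.** Section 11 (Statistical Considerations) describes a pre-post paired comparison and gives the plan's only power figures. The first is "With a total of 20 subjects we will have 90% power to detect a 0.1% unit change in intramyocardial lipid content". It is based on an "estimated within subject standard deviation of MRS intramyocardial lipid of 0.07" (in percent units), taken from a cited spectroscopy study.

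Section 11 then recalls mean lipid contents of 1.5% in HIV-infected subjects and 1.0% in controls from the team's earlier work, and concludes that "we will have ample power to detect a minimal clinically relevant reduction of 0.3% units or greater following eplerenone therapy".

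Section 11.1 fixes the test: "This will be tested using a paired t-test, and a two sided p value of < 0.05 will be used". The Précis fixes the time points: "Magnetic resonance imaging will be conducted at screening and the final study visit to evaluate cardiac and hepatic steatosis".

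On losses, Section 10.10 says: "If a subject withdraws after fewer than 12 weeks of study treatment, then they will be replaced". No dropout rate is given. Section 3.1 explains the size of the study: "This is a proof of concept study and therefore the sample size will be relatively small".

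**The concern.** There are two separate points.

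**A. The arithmetic.** A change of 0.1% is larger than the quoted SD of 0.07%. With 20 pairs, a standardised effect of that size should give power well above 90%.

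**B. The SD behind the 0.3% assurance.** A paired t-test depends on the SD of the individual changes from screening to Week 24. That SD includes scan error, and also real fluctuation over about six months and differences between subjects in response. The plan gives a within-subject SD but does not say whether it refers to one scan or to a difference, or over what interval it was obtained. It gives no SD of the 24-week change and no pre-post correlation.

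Sections 3.1 and 7.2 make the decision on a larger trial depend on what this study shows. A reader of a null cardiac result needs to know what change the study could have detected, and under what SD.

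**Working it through.** **Inputs.** n = 20, change 0.1% and 0.3%, SD 0.07% (Section 11); paired t-test, two-sided 0.05 (Section 11.1).

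**Formula.** Exact power from the noncentral t distribution with n − 1 degrees of freedom and noncentrality δ / SD_diff × √n.

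**Step 1. Try to reproduce the stated 90% (δ = 0.1, n = 20).**

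| Reading of 0.07% | SD_diff | Noncentrality | Power |
|---|---|---|---|
| SD of a single scan | 0.07 × √2 = 0.099 | 0.1/0.099 × √20 = 4.52 | 99.0% |
| SD of the difference | 0.07 | 0.1/0.07 × √20 = 6.39 | >99.9% |

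With 18 pairs the figures are 98.1% and >99.9%.

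Variants under the single-scan reading, which gives the lower power:

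- normal approximation: 99.5%
- one-sided 0.05: 99.7%
- two-sided 0.025: 97.5%
- SD anywhere from 0.065% to 0.075%, to allow for rounding: 99.6% to 97.9%

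None of these gives 90%. On the stated inputs, 13 subjects (91.6%) or 8 subjects (93.1%) would already exceed 90% under the two readings.

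**Step 2. What SD would give 90%?** At n = 20, 90% power needs a standardised effect of 0.7645. So SD_diff = 0.1 / 0.7645 = 0.131%. The plan does not state this value.

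**Step 3. The 0.3% assurance.** If SD_diff is 0.07%, 0.099% or even 0.131%, power for 0.3% exceeds 99.9% with 20 pairs. The largest SD of change that keeps the power is 0.3 divided by the standardised effect required:

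| Evaluable pairs | Effect for 90% / 80% | Largest SD for 90% / 80% |
|---|---|---|
| 20 | 0.7645 / 0.6604 | 0.392% / 0.454% |
| 18 | 0.8112 / 0.7007 | 0.370% / 0.428% |
| 16 | 0.8677 / 0.7495 | 0.346% / 0.400% |

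The limit of 0.392% is 0.392/0.099 = 4.0 times the single-scan reading and 0.392/0.07 = 5.6 times the other. The margin is therefore wide if the quoted SD carries over to the 24-week change.

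**Step 4. Power for 0.3% at larger SDs of change.** The first two rows are the rounded limits from Step 3. The last three are assumed values, because the documents give none.

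| SD of change | 20 pairs | 18 pairs |
|---|---|---|
| 0.39% | 90% | 87% |
| 0.45% | 81% | 76% |
| 0.3% (assumed) | 99% | 98% |
| 0.4% (assumed) | 89% | 85% |
| 0.5% (assumed) | 72% | 67% |

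**Step 5. The only other spread in the documents.** Section 1.1.1 gives 1.5% ± 1.2% for intramyocardial lipid in HIV-infected subjects. Assume that the ± is an SD and that it holds at both time points. Then SD_diff = 1.2 × √(2(1 − ρ)), and 90% power for 0.3% needs ρ of at least 1 − (0.392/1.2)²/2 ≈ 0.95. Under the same assumption, ρ = 0.9 gives 66% and ρ = 0.8 gives 39%. This shows that the condition is not trivial. It does not show that the condition fails.

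**The case against.** **The 90% may be loose wording rather than a wrong calculation.** With n = 20, the change detectable at 90% power is 0.7645 × 0.099 = 0.076% or 0.7645 × 0.07 = 0.054%. Both round to 0.1% at the one-decimal precision used for effects in Section 11. The figure might also mean at least 90%. Either is possible, but the text says neither, and as written it is inexact. A two-group formula with 10 per group and SD 0.07% gives 89.1% by normal approximation, but Section 3.1 says there is no control arm.

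**Point A has no consequence for the design.** This is true. The error understates power, and no sample size, test or endpoint depends on it.

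**Printing 99% could over-assure, since point B doubts the same SD.** This is a fair caution. The corrected figure must carry the condition that the SD applies to the screening-to-Week-24 change.

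**Point B shows no shortfall, and the loss of pairs is hypothetical.** The first part stands: on the plan's own SD the margin is four- to almost six-fold. On losses, the accrual ceiling of 50 and the replacement of early withdrawals help. But withdrawals from Week 12 onward are not replaced, and Section 6.6 leaves the assessments at an early termination visit to judgement. A second MRI is therefore not assured. The 18- and 16-pair rows are illustrations, not forecasts.

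**Conclusion.** Both points hold.

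**A** is an arithmetic error in the conservative direction: 90% stated, against 99.0% or above 99.9% on the plan's own inputs and test. The result rests only on figures in Sections 11 and 11.1 and covers both readings of the SD.

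**B** is an unsupported assumption. The 0.3% statement is right if 0.07% describes variation over 24 weeks. It keeps 90% power with 20 evaluable pairs as long as the SD of change is no more than about 0.39%, and 80% as long as it is no more than about 0.45%. The documents do not settle whether that condition is met.

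Neither point challenges the choice of 20 subjects for a proof-of-concept study. The passage should be corrected because it is the plan's only account of what the study can detect.

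**What to change.** Keep 20 subjects and amend Section 11 as follows.

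1. State whether 0.07% is the SD of a single scan or of the difference, and replace the 90% statement with, for example:

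> *With 20 evaluable pairs, power for a 0.1% unit change is 99.0% [if per scan] / above 99.9% [if of the difference], provided this SD applies to the screening-to-Week-24 change.*

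2. Replace the unqualified assurance for 0.3% with:

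> *With 20 evaluable pairs, power for a 0.3% unit reduction is at least 90% if the SD of the 24-week change is at most 0.39%, and at least 80% if it is at most 0.45%. Power is lower with fewer evaluable pairs; for example, 18 pairs at an SD of 0.39% give about 87%.*

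3. If a table over larger SDs is added, keep it short and label the values as assumed.

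As an option, not required by the power error, report the mean change and its SD, with a 95% confidence interval set against 0.3%.

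The cost is protocol and SAP wording only: no extra patients, visits or scans, and no change of endpoint or test. The drawback is that the 0.3% assurance becomes conditional.

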11.1. Statistical Analysis Plan

As previously stated, the primary endpoints for this study will be change in cardiac and hepatic steatosis from initial measurement (pre-treatment) to end of study measurement. This will be tested using a paired t-test, and a two sided p value of < 0.05 will be used for detection of

significance. In addition, we will conduct exploratory analyses to determine if eplerenone therapy is associated with changes in biomarkers of inflammation (eg, MCP-1 and IL-6). We also plan to evaluate potential changes in visceral fat volume with treatment, but these will be exploratory analyses, primarily descript, and which may not be sufficiently powered in this small preliminary trial. Finally we will construct descriptive tables summarizing reported side effects and any observed lab abnormalities observed during the course of study participation in all subjects.

12. Ethics/Protection of Human Subjects

12.1. Informed Consent Process

Informed consent is a process where information is presented to enable persons to voluntarily decide whether or not to participate as a research subject. It is an ongoing conversation between the human research subject and the researchers which begins before consent is given and continues until the end of the subject's involvement in the research. Discussions about the research will provide essential information about the study and include: purpose, duration, experimental procedures, alternatives, risks and benefits. Subjects will be given the opportunity to ask questions and have them answered.

The subjects will sign the informed consent document prior to undergoing any research procedures. The subjects may withdraw consent at any time throughout the course of the trial. A copy of the informed consent document will be given to the subjects for their records. The researcher will document the signing of the consent form in the subject's medical record. The rights and welfare of the subjects will be protected by emphasizing to them that the quality of their medical care will not be adversely affected if they decline to participate in this study.

12.1.1. Non-English-Speaking Subjects

If a non-English-speaking subject is unexpectedly eligible for enrollment, the subject will be provided with the CC Short Written Consent Form for Non-English-Speaking Research Subjects in the subject's native language and a verbal explanation of the purpose, procedures, and risks of the study as described in MAS Policy M77-2, NIH HRPP SOP 12, and 45 CFR 46.117(b)(2). If the CC Short Written Consent Form is used three times or more for the same language, this will be reported to the IRB immediately.

12.2. Subject Confidentiality

All records will be kept confidential to the extent provided by federal, state and local law. The study monitors and other authorized representatives of the Sponsor may inspect all documents and records required to be maintained by the Investigator, including but not limited to, medical records. Records will be kept locked and all computer entry and networking programs will be done with coded numbers only. Clinical information will not be released without written permission of the subject, except as necessary for review by IRB or the OHRP.

13. Data Handling and Record Keeping

13.1. Data Capture and Management

Study data will be maintained in CRIMSON and collected directly from subjects during study visits and telephone calls, or will be abstracted from subjects' medical records. Source documents include all recordings of observations or notations of clinical activities and all reports and records necessary to confirm the data abstracted for this study. Data entry into CRIMSON will be performed by authorized individuals. The Investigator is responsible for assuring that the data collected are complete, accurate, and recorded in a timely manner.

13.2. Record Retention

The investigator is responsible for retaining all essential documents listed in the ICH GCP Guideline. Study records will be maintained by the PI for a minimum of 5 years and in compliance with institutional, IRB, state, and federal medical records retention requirements, whichever is longest. All stored records will be kept confidential to the extent required by federal, state, and local law.

Appendix B: Schedule of Procedures/Evaluations

Evaluation	Screening	Baseline Day 0	Safety Visits (Weeks 1, 2, 4, 8, 18)	Interim Visit (Week 12)	Final Study Visit (Week 24)
Physical exam, medical history	X ^a	X	X	X	X
Vital signs ^b	X	X	X	X	X
Urine pregnancy test ^c	X	X	X	X	X
Research blood collection	X	X	X	X	X
Urine collection	X				
Cardiac and hepatic MRI	X				X
Transient elastography ^d	X				X
Liver biopsy ^e	X				X
Bionutrition ^f	X				X

Appendix C: Prohibited Medications

Strong CYP3A4 Inhibitors	
• Boceprevir• Clarithromycin• Conivaptan• Grapefruit juice• Indinavir• Itraconazole• Ketoconazole	
• Lopinavir/ritonavir• Mibefradil• Nefazodone• Nelfinavir• Posaconazole• Ritonavir	
• Saquinavir• Seville oranges• Suboxone• Telaprevir• Telithromycin• Voriconazole
Strong CYP3A4 Inducers	
• Avasimibe• Carbamazepine• Phenytoin	
• Rifampin• Rifabutin	
• Rifapentine• St. John's wort
Potassium-Sparing Diuretics	
• Amiloride• Spironolactone• Triameterene		
Agents that May Cause Hyperkalemia	
• Aliskerin• Cyclosporine• Digoxin	
• Penicillin G• Pentamidine	
• Tacrolimus• Verapamil

CYP = cytochrome P450 isozyme; NSAID = nonsteroidal anti-inflammatory drug.
